2. STUDY OBJECTIVES AND ENDPOINTS

Study objectives and endpoints are presented in [Table 2](#).

Table 2: Study Objectives and Endpoints

Primary Objectives	Primary Endpoints
Phase 1:	
To evaluate the safety, tolerability, and DLTs and to define a MTD and/or PAD of epacadostat in combination with nivolumab and ipilimumab, and in combination with nivolumab and lirilumab, in subjects with advanced or metastatic solid tumors.	Safety and tolerability will be assessed by monitoring frequency, duration, and severity of AEs through physical examinations, by evaluating changes in vital signs and ECGs, and through clinical laboratory blood and urine sample evaluations.
Phase 2:	
Treatment Group A: To evaluate the efficacy of epacadostat in combination with nivolumab and ipilimumab in subjects with advanced or metastatic NSCLC and unresectable or metastatic MEL by assessing ORR per RECIST v1.1.	ORR, defined as the percentage of subjects having CR or PR, will be determined by investigator evaluation of radiographic disease assessment per RECIST v1.1.
Treatment Group B: To evaluate the efficacy of epacadostat in combination with nivolumab and lirilumab in subjects with recurrent or metastatic SCCHN by assessing ORR per RECIST v1.1.	
Secondary Objectives	Secondary Endpoints
Phase 1:	
To evaluate the efficacy of epacadostat in combination with nivolumab and ipilimumab, and in combination with nivolumab and lirilumab, in subjects with advanced or metastatic solid tumors by assessing ORR per RECIST v1.1.	ORR, defined as the percentage of subjects having CR or PR, will be determined by investigator evaluation of radiographic disease assessment per RECIST v1.1.
Phase 1 and Phase 2:	
To evaluate the efficacy of epacadostat in combination with nivolumab and ipilimumab, and in combination with nivolumab and lirilumab, in subjects with advanced or metastatic solid tumors in Phase 1 and in subjects with selected advanced or metastatic solid tumors in Phase 2 by assessing DOR and PFS per RECIST v1.1.	DOR is defined as the time from the earliest date of CR or PR until the earliest date at which progression criteria are met as determined by investigator evaluation of radiographic disease assessment per RECIST v1.1, or date of death due to any cause.

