4.1.1. Phase 1 – Dose Escalation

Dose escalation in Treatment Groups A and B will be conducted using a standard 3 + 3 + 3 design as per the dose-escalation schedule outlined in Table 3. A minimum of 3 evaluable subjects will be enrolled in each treatment group beginning with Dose Level 1 (starting dose of epacadostat 50 mg BID in Treatment Groups A and B).

In Treatment Group A, the first 3 evaluable subjects at each dose level will be observed for a minimum of 42 days before the next dose level begins enrollment. To be evaluable for tolerability, subjects must receive at least 75% of planned epacadostat doses (63/84) at the specified dose level, 3 doses of nivolumab, and 1 dose of ipilimumab, or subjects must experience a DLT during the DLT observation period.

In Treatment Group B, the first 3 evaluable subjects at each dose level will be observed for a minimum of 42 days before the next dose level begins enrollment. To be evaluable for tolerability, subjects must receive at least 75% of planned epacadostat doses (63/84) at the specified dose level, 3 doses of nivolumab, and 2 doses of lirilumab, or subjects must experience a DLT during the DLT observation period.

Subjects who discontinue for reasons other than a DLT (eg, events clearly associated with the underlying disease, disease progression, concomitant medication, comorbidity, or an AE clearly

unrelated to study treatment) during a DLT observation period will be considered nonevaluable for DLT evaluation and will be replaced.

Alternate doses or dose administration schedules, including sequenced (rather than concurrent) administration of treatment components, [REDACTED] and safety results.

For both treatment groups, the following dose-escalation rules apply:

- If 0 of the first 3 evaluable subjects at a dose level have a DLT, 3 subjects will be enrolled and treated at the next higher dose level (if applicable).
- If 1 of the first 3 evaluable subjects at a dose level has a DLT, that dose level will be expanded to 6 subjects. If ≤ 1 of 6 subjects in a dose level has a DLT, 3 subjects will be enrolled and treated at the next higher dose level (if applicable).
- If 2 of 6 subjects at a dose level have a DLT, that dose level will be expanded to include 9 subjects.
- If ≥ 2 of 3, ≥ 3 of 6, or ≥ 3 of 9 subjects have DLTs at a specific dose level, that dose level will be determined to have exceeded the MTD, and the previous dose level will be considered the MTD.

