4.3.2. Replacement of Subjects

Subjects may be replaced for any of the following reasons:

- In Phase 1, any subject who withdraws from treatment before the completion of the DLT observation period for any reason other than a DLT (ie, is not evaluable for DLTs; see Section 5.4.2) or who does not have the required exposure to the study drugs during the DLT evaluation period, may be replaced to ensure a minimum number of evaluable subjects.
- Subjects who do not meet the eligibility requirements of the study may be replaced.

Subjects who meet any of the criteria for replacement may remain on study for evaluation as outlined in Section 9.1 and Section 9.2.

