5.4.2. Dose-Limiting Toxicity and Determination of Maximum Tolerated Dose

A DLT will be defined as the occurrence of any of the toxicities in [Table 7](#) occurring from Cycle 1 Day 1 up to and including Day 42 for Treatment Groups A and B in Phase 1, except those with a clear alternative explanation (eg, disease progression) or transient (≤ 72 hours) abnormal laboratory values without associated clinically significant signs or symptoms based on investigator determination. Immune-related AEs of Grade 3 that improve to Grade 1 or lower within 14 days after the initiation of supportive care or corticosteroid therapy may be deemed a non-DLT. All DLTs will be assessed by the investigator using CTCAE v4.03 criteria.

To be evaluable for tolerability, subjects in Treatment Group A must receive at least 75% of planned epacadostat doses (63/84) at the specified dose level, 3 doses of nivolumab, and 1 dose of ipilimumab, or subjects must experience a DLT during the DLT observation period. Subjects in Treatment Group B must receive at least 75% of planned epacadostat doses (63/84) at the specified dose level, 2 doses of nivolumab, and 2 doses of lirilumab, or subjects must experience a DLT during the DLT observation period.

Individual subject dose reductions may be made based on events observed at any time during treatment with study drug; however, for the purposes of dose cohort escalation/de-escalation, expanding a dose cohort, and determining the MTD of epacadostat, decisions will be made based on events that are observed from the first day of study drug administration through the above-defined DLT observation period for each treatment group. A lower MTD may subsequently be determined based on relevant toxicities that become evident after the DLT observation period.

Table 7: Definition of Dose-Limiting Toxicity

Toxicity
Nonhematologic

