9. STATISTICS

9.1. Study Populations

The safety population includes all subjects enrolled in the study who received at least 1 dose of combination therapy (epacadostat, nivolumab, ipilimumab for Treatment Group A, or epacadostat, nivolumab, lirilumab for Treatment Group B). All safety analyses will be based on the safety population.

The full analysis set includes all subjects enrolled in the study who received at least 1 dose of combination therapy (epacadostat, nivolumab, ipilimumab for Treatment Group A, or epacadostat, nivolumab, lirilumab for Treatment Group B). The full analysis set will be used for the summary of demographics, baseline characteristics, subject disposition, and analyses of all efficacy data.

The PP population includes all subjects in the full analysis set that are considered to be sufficiently compliant with the Protocol. More details of the PP population will be provided in the Statistical Analysis Plan. The PP population may be used in the sensitivity analysis of efficacy endpoints. The determination of subjects being considered for exclusion from the PP population by the clinical team will be prepared and signed before database freeze.

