9.4. Statistical Analyses

Note: As Amendment 2 will serve to discontinue the study to further enrollment, limited safety and efficacy analyses will be performed. Listings will be substituted for summary tables for efficacy analyses. Summary tables will only be provided for selected safety analyses.

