9.4.2. Safety Analyses

The clinical safety data (vital signs, physical examinations, ECGs, laboratory tests, and AEs) will be summarized using descriptive statistics (eg, mean, frequency) using the safety population. Summary tables may be replaced with listings when appropriate. For example, an AE frequency table may be replaced with a listing if it only contains a few unique preferred terms reported on relatively few subjects.

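### Does Section 9 leave dose-limiting toxicities without an analysis set, so that the reported DLT rate could be diluted?

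*Combined protocol and SAP*

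**What the plan says.** The Phase 1 primary objective in Section 2, Table 2, is "To evaluate the safety, tolerability, and DLTs and to define a MTD and/or PAD of epacadostat" with each antibody pair. The endpoint beside it covers adverse events (AEs), vital signs, ECGs and laboratory tests, and does not mention DLTs.

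Sections 4.1.1 and 5.4.2 say how DLTs are counted. In Treatment Group A an evaluable subject has taken at least 63 of 84 planned epacadostat doses, 3 nivolumab doses and 1 ipilimumab dose, or has had a DLT. Subjects who stop within the observation period for another reason "will be considered nonevaluable for DLT evaluation and will be replaced". Among other triggers, a level exceeds the MTD if "≥ 3 of 9 subjects have DLTs at a specific dose level". Under Section 4.3.2, replaced subjects "may remain on study for evaluation as outlined in Section 9.1 and Section 9.2".

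Section 9.1 defines a safety population, a full analysis set and a per-protocol population. The first two require at least one dose of combination therapy. Section 9.1 adds: "All safety analyses will be based on the safety population". In Section 9.4.2, data on AEs, laboratory tests, ECGs, vital signs and physical examinations "will be summarized using descriptive statistics (eg, mean, frequency) using the safety population". The Note that Amendment 2 added to Section 9.4 says: "Summary tables will only be provided for selected safety analyses".

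**The concern.** A primary-objective quantity seems to have no analysis set and no planned output. The sentence in 9.1 has no exception, and 4.3.2 sends replaced subjects to 9.1, where any who were dosed enter the safety denominator. A DLT rate by dose level calculated that way would fall below the rate on which the escalation rule acted. The Note in 9.4 names none of the tables it keeps, so a DLT table might also be left out.

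Ordinary AE tables would not replace it. DLTs are limited to the first 42 days, and Table 7 exempts several kinds of Grade 3 event, so a DLT count cannot be read from a table of treatment-emergent events. At stake is whether a reader of the report could see the result that supported the dose conclusion.

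**Working it through.** **1. The plan's own figure.** The observation period is 42 days with twice-daily dosing (Sections 4.1.1 and 5.4.2): 42 × 2 = 84 planned doses, and 0.75 × 84 = 63. The stated 63/84 is exactly 75%, so the Group A rule is well defined.

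**2. The passages side by side.**

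| Question | Where answered | Answer |
|---|---|---|
| Who counts for DLTs? | 4.1.1, 5.4.2 | Evaluable subjects, by exposure or by having a DLT |
| What of early stoppers without a DLT? | 4.1.1, 4.3.2 | Not evaluable for DLTs; replaced |
| Which events set the MTD? | 5.4.2 | Those in the DLT observation period, though later toxicity may lower it |
| Which data use the safety population? | 9.4.2 | AEs, laboratory tests, ECGs, vital signs, physical examinations |
| Is a DLT rate on all treated subjects called for? | Visible Section 9 | No; DLTs appear only in the sample-size text of 9.2.1 |

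The general sentence in 9.1 and the specific rules in 4.1.1, 4.3.2 and 5.4.2 can stand together. AEs are reported on everyone treated, which is right for replaced subjects too; DLTs are counted among evaluable subjects. A conflict arises only if the general sentence is taken to override the specific ones.

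**3. Size if it were read that way.** Let x be the number of DLTs, E the evaluable subjects and R the treated subjects replaced at a dose level. The two rates are x/E and x/(E + R), so the second is the first multiplied by E/(E + R). The documents do not give R; 0 to 3 is an assumption. For x = 3 and E = 9, a level that exceeds the MTD:

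| R | Rate | Exact 95% interval |
|---|---|---|
| 0 | 3/9 = 33.3% | 7.5% to 70.1% |
| 1 | 3/10 = 30.0% | 6.7% to 65.2% |
| 2 | 3/11 = 27.3% | 6.0% to 61.0% |
| 3 | 3/12 = 25.0% | 5.5% to 57.2% |

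The largest shift shown is 33.3 − 25.0 = 8.3 percentage points. The interval at R = 0 is 70.1 − 7.5 = 62.6 points wide.

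This takes x to be the same in both sets. That holds if one dose of any component admits a subject to the safety population. Section 9.1 does not say whether all three drugs are needed; if they are, a subject with a DLT before the ipilimumab infusion would be evaluable but outside that population.

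Table 7 also narrows R. Being unable, because of toxicity, to take 75% of doses is itself a DLT, apart from the listed exceptions.

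**4. Effect on decisions.** The thresholds in 4.1.1 are counts among evaluable subjects. The choice of population in Section 9 cannot change whether a level was declared above the MTD. Applying those thresholds also means that the number of DLTs and the number evaluable were established at each decision, so the figures for a DLT summary exist.

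**The case for a change.** The best case for a change is that 9.1 is visible, unqualified and part of the statistical section, whereas the evaluability rule is written for escalation and never carried across. Section 9 defers to the SAP for the per-protocol set and for censoring of progression-free survival, but not for DLTs, so an SAP using evaluable subjects would depart from the letter of 9.1. Section 9.3 calls Phase 1 exploratory, which removes formal tests but not the need for a denominator. With efficacy reduced to listings, the safety tables carry more of the report.

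Part of this stands. The cross-reference is missing, the retained tables are unnamed, and AE tables cannot reproduce a DLT count. But the argument needs two things at once: that no DLT summary is planned, and that one would be produced on the wrong denominator. The documents support neither firmly. Text after 9.4.2.5 and two contents entries there are blacked out, so a missing DLT output is not proven; and no passage asks for a DLT rate on all treated subjects. Replacing tables with listings is a stated choice, and 9.4.2.1 keeps every AE in the listings.

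Sections 4.1.1 and 5.4.2 do disagree on the nivolumab doses needed for evaluability in Treatment Group B (3 against 2), and those passages need reconciling. That is a separate matter with no bearing here, because nobody entered Group B.

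**Conclusion.** No change to the plan is called for. The observation is accurate: Section 9.1 names no DLT-evaluable set, and the visible part of Section 9 specifies no DLT summary. It is a gap in detail that an analyst would fill from Section 5.4.2, reporting Group A DLTs by dose level over evaluable subjects and giving the numbers treated and replaced. Dose and MTD conclusions do not depend on it.

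The illustrated dilution, at most 8.3 percentage points for 3 of 9, assumes up to three replacements at a level and an output that no visible text requests. With no replacements it is zero. Enrollment is closed, so formal protocol wording would gain little over a sentence in the analysis documentation.

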9.2. Selection of Sample Size

9.2.1. Sample Size in Phase 1

A 3 + 3 + 3 dose escalation design will be used in Phase 1 to determine the MTD or PAD and DLT(s) of epacadostat when given in combination with nivolumab and ipilimumab (Treatment Group A) and nivolumab and lirilumab (Treatment Group B). The total number of subjects will depend on the frequency of DLTs and number of dose levels tested before MTD or PAD is established. Based on 3 + 3 + 3 design algorithm, within each treatment group, a minimum of 3 subjects and up to 9 subjects will be enrolled at each dose level.

9.2.2. Sample Size in Phase 2

The Phase 2 dose expansions will evaluate the efficacy and further evaluate the safety, tolerability, [REDACTED] of the MTD or PAD of epacadostat determined in each of the Phase 1 treatment groups in select solid tumors. A sample size of 35 subjects is expected to be enrolled in Cohorts A1, A2, and B1 (Table 30). The sample size for the Cohort A1 (MEL) yields a power of 80% to detect a target ORR of about 20% increase (Ha: 79%) from historical response rate (H0: 59%). For Cohort A2 (NSCLC), this yields a power of 80% to detect a target ORR of about 22% increase (Ha: 52%) from historical response rate (H0: 30%). For Cohort B1 (SCCHN), this yields a power of 80% to detect a target ORR of about 22% increase (Ha: 46%) from historical response rate (H0: 24%). This assumes a 1-sided alpha of 5%. Subjects who undergo serial prestudy and on-treatment tumor biopsies in expansion Cohorts A1, A2, and B1 may be at risk of being nonevaluable for response; therefore, additional subjects may be enrolled in a specific efficacy expansion cohort to achieve a minimum 35 response-evaluable subjects.

Table 30: Sample Size Calculation for Each Phase 2 Cohort: Comparing to a Known Proportion

Efficacy Expansion Cohort	H0	Ha	Sample Size
MEL (A1)	59%	79%	35
NSCLC (A2)	30%	52%	35
SCCHN (B1)	24%	46%	35

9.3. Level of Significance

Phase 1 of the study is exploratory and no formal statistical tests will be performed. Unless otherwise specified, all CIs will be at the 95% confidence level.

The level of significance for each of the Phase 2 cohorts (A1, A2, and B1) is 1-sided 5% for the analysis of the primary endpoint of ORR.

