
Statistical Methods: Phase 1 of the study will use a 3 + 3 + 3 design to evaluate the safety of epacadostat in combination with nivolumab and ipilimumab (Treatment Group A) and in combination with nivolumab and lirilumab (Treatment Group B) in subjects with advanced or metastatic solid tumors. During the Phase 1 portion of the study, the sample size at each dose level depends on the number of observed toxicities. Between 3 and 9 subjects are expected to be treated at each dose level. Phase 2 expansion cohorts will evaluate the efficacy and further evaluate the safety, tolerability, [REDACTED] of the MTD or PAD of epacadostat determined in each of the Phase 1 treatment groups in select solid tumors. A sample size of 35 subjects is expected to be enrolled in each of the Phase 2 expansion cohorts (A1, A2, and B1). This sample size for Cohort A1 (MEL) yields a power of 80% to detect a target ORR of about 20% increase (Ha: 79%) from historical response rate (H0: 59%). For Cohort A2 (NSCLC), this yields a power of 80% to detect a target ORR of about 22% increase (Ha: 52%) from historical response rate (H0: 30%). For Cohort B1 (SCCHN), this yields a power of 80% to detect a target ORR of about 22% increase (Ha: 46%) from historical response rate (H0: 24%). This assumes a 1-sided alpha of 5%. Subjects who undergo serial prestudy and on-treatment tumor biopsies in expansion Cohorts A1, A2, and B1 may be at risk of being nonevaluable for response; therefore, additional subjects may be enrolled in a specific efficacy expansion cohort to achieve a minimum 35 response-evaluable subjects.
 
The clinical safety data (eg, vital signs, ECGs, laboratory tests, AEs) will be descriptively summarized. The ORR will be summarized with 95% exact binomial confidence interval (CI), if appropriate. Kaplan-Meier estimates of median DOR, PFS, and OS will be provided with 95% CIs.

Safety Monitoring Committee: A Safety Monitoring Committee (SMC) will review safety data at regular intervals throughout Phase 2. Details regarding SMC membership and roles and responsibilities of the committee will be specified in the SMC charter.

TABLE OF CONTENTS

SYNOPSIS	3
LIST OF ABBREVIATIONS.....	22
1. INTRODUCTION	25
1.1. Background.....	25
1.1.1. The Role of the Immune System in Cancer and Overall Study Rationale	25
1.1.2. Inhibition of Indoleamine 2,3-Dioxygenase 1 as a Target for Cancer	25
1.1.3. Inhibition of Killer Cell Immunoglobulin-Like Receptors as a Target for Cancer	26

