4. INVESTIGATIONAL PLAN

4.1. Overall Study Design

Note: Amendment 2 will serve to close the study to further enrollment; the primary purpose of the amendment is to provide an updated assessment schedule for subjects enrolled to date (Treatment Group A only). No subjects were enrolled into Treatment Group B.

[figure not shown]
This is an open-label, nonrandomized, Phase 1/2 study to determine the safety, tolerability, and efficacy of epacadostat when given in combination with nivolumab and ipilimumab, and in combination with nivolumab and lirilumab. The study will be conducted in 2 independent treatment groups: Treatment Group A will evaluate the combination of epacadostat, nivolumab, and ipilimumab; Treatment Group B will evaluate the combination of epacadostat, nivolumab, and lirilumab. Each treatment group will be investigated in 2 phases:

- Phase 1 will consist of a standard 3 + 3 + 3 dose-escalation design to define the MTD or PAD of epacadostat with nivolumab and ipilimumab (Treatment Group A) and with nivolumab and lirilumab (Treatment Group B) in subjects with advanced or metastatic solid tumors; [REDACTED]
- Phase 2 will evaluate the efficacy of the MTD or PAD of epacadostat when given in combination with nivolumab and ipilimumab, and in combination with nivolumab and lirilumab, as determined in each of the Phase 1 treatment groups in select solid tumors, and will further evaluate the safety, [REDACTED] of the combinations.

Treatment Group A will enroll 2 tumor-specific expansion cohorts (Cohorts A1 and A2); Cohort A1 will include subjects with unresectable or metastatic MEL who have not received prior systemic therapy for advanced or metastatic disease; Cohort A2 will include subjects with advanced or metastatic NSCLC who have received no more than 1 prior line of platinum-based chemotherapy for advanced or metastatic disease.

Treatment Group B will enroll 1 expansion cohort (Cohort B1); Cohort B1 will include subjects with recurrent or metastatic SCCHN who have received no more than 1 prior line of platinum-based chemotherapy for recurrent or metastatic disease. See [Figure 1](#) for overall study design.

Figure 1: Study Design

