6.4. Follow-Up

6.4.1. Safety Follow-Up

The safety follow-up period is the interval between the EOT visit and the scheduled follow-up visits, which should occur approximately 30 days (+ 7 days), 100 days (\pm 7 days), and 150 days

(± 7 days; Treatment Group B only) after the EOT visit (or after the last dose of study treatment if the EOT visit was not performed). Adverse events and SAEs must be reported up until at least 100 days after the last dose of study treatment for Treatment Group A, up until at least 150 days after the last dose of study treatment for Treatment Group B, or until toxicities resolve, return to baseline, or are deemed irreversible, whichever is longer. Reasonable efforts should be made to have the subject return for the follow-up visits and to report any AEs that may occur during this period. If a subject is scheduled to begin a new anticancer therapy before the end of the safety follow-up period, the applicable safety follow-up visit should be performed before new anticancer therapy is started. After the safety follow-up period, there will be no additional assessments and the study will be considered complete.

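### Does Amendment 2 leave it open whether the 1-sided 5% test of ORR in the Phase 2 cohorts still applies?

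*Combined protocol and SAP*

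**What the plan says.** Several places in the protocol bear on the point.

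- **Section 9.3** sets the error rate for the primary endpoint: "The level of significance for each of the Phase 2 cohorts (A1, A2, and B1) is 1-sided 5" (per cent). It also says that Phase 1 carries no formal tests.
- **Section 9.2.2 with Table 30** gives the planning. The null and target response rates are 59% and 79% (A1), 30% and 52% (A2), and 24% and 46% (B1), with 35 subjects in each cohort. "The sample size for the Cohort A1 (MEL) yields a power of 80" (per cent); the same is claimed for A2 and B1. On the error rate: "This assumes a 1-sided alpha of 5" (per cent).
- **Section 9.4** opens with the Amendment 2 note. Because enrollment stops, safety and efficacy analyses are limited, and "Listings will be substituted for summary tables for efficacy analyses". Section 9.4.1, directly beneath, keeps its text on ORR with exact 95% intervals and on Kaplan-Meier estimates of PFS and DOR.
- **Synopsis, Statistical Methods** repeats the power and the alpha without mentioning the limitation. It adds "The ORR will be summarized with 95% exact binomial confidence interval (CI), if appropriate" and "Kaplan-Meier estimates of median DOR, PFS, and OS will be provided with 95% CIs".
- **Section 4.1** reports the closure of enrollment and states: "No subjects were enrolled into Treatment Group B".
- **Section 6.4.1** ends data collection with the safety follow-up, whose last visit in Group A is at 100 days: "After the safety follow-up period, there will be no additional assessments and the study will be considered complete".

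**The concern.** Read in order, 9.2.2 and 9.3 describe a live confirmatory test in three cohorts, and the next section replaces efficacy tables with listings. One of the three cohorts is empty. The 9.4 note speaks of the extent and format of output. It does not mention the hypothesis, the alpha or the power. A reader could therefore hold that the test stands, or that it has lapsed, and cite the protocol either way.

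The study is open-label and response is assessed by the investigator. If the status of the primary test were truly open, a favorable cohort could be reported as a formal success and an unfavorable one left as a listing, with the choice made after the data were seen. The 80% power might also be quoted for a cohort that closed well short of 35. The synopsis adds to the confusion by promising median DOR, PFS and OS, which listings do not supply.

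**Working it through.** **1. Are the design figures right?** Inputs are from 9.2.2, Table 30 and 9.3: n = 35, 1-sided alpha 0.05, and p0 and p1 as listed above. The test is the exact one-sample binomial. The critical count r is the smallest integer with P(X ≥ r | 35, p0) ≤ 0.05, and power is P(X ≥ r | 35, p1).

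| Cohort | p0 | p1 | r | Attained alpha | Power |
|---|---|---|---|---|---|
| A1 | 0.59 | 0.79 | 26 | 4.5% | 81.6% |
| A2 | 0.30 | 0.52 | 16 | 3.6% | 81.9% |
| B1 | 0.24 | 0.46 | 14 | 2.6% | 81.1% |

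One response fewer would breach 5% in each cohort (9.1%, 7.3% and 5.7%). The stated 80% reproduces, so nothing in 9.2.2 needs correcting.

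**2. Does the power depend on reaching exactly 35?** Close to 35 the answer is clouded by the discreteness of the binomial. For A1, power at n = 32, 33, 34, 35, 36, 37 and 38 is 78.5%, 75.6%, 72.6%, 81.6%, 79.1%, 76.4% and 84.3%. It falls below 80% at 36 and 37 as well, which are larger than planned, so a dip at 34 shows no special fragility. At much smaller n the loss is real. The documents do not give Phase 2 enrollment, so the following sizes are assumptions.

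| Assumed n | A1 power | A2 power |
|---|---|---|
| 10 | 34.6% | 42.7% |
| 20 | 58.6% | 65.7% |
| 30 | 71.5% | 77.9% |

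This is a reason not to quote 80% for a short cohort. It does not make the plan wrong, because 9.2.2 states what 35 subjects would give.

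**3. What does the 9.4 note cover?** The alpha in 9.3 is attached to the analysis of ORR. That is an efficacy analysis, and the 9.4 note governs efficacy analyses. A subject-level listing gives no rejection decision. Following 9.4 as written therefore means that no test is reported, and the note takes precedence over the older wording of 9.4.1 beneath it.

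**4. Could a false claim result from the leftover wording?** Suppose the test were run on the actual n. The critical count is chosen so that P(X ≥ r | n, p0) ≤ 0.05 for whatever n applies. If closure did not depend on this study's responses, the false-positive rate per cohort stays at or below 5%, and leaving a non-rejection unreported does not raise it. Only power is lost. In B1, n = 0 and no test exists. If A1 and A2 also received no one, which the documents neither confirm nor exclude, 9.3 has nothing to act on.

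**5. Is the OS sentence impossible to honor?** No. Section 6.4.1 stops assessments after safety follow-up, but 6.5 asks sites to make every effort to obtain dates of death. An OS curve censored at last contact could be drawn, though it would be short and heavily censored. The mismatch is with the listings note. Appendix F names the synopsis, 4.1 and 9.4 together as the places for the Amendment 2 note, which suggests that the synopsis statistics paragraph was simply not brought into line.

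**The case for a change.** The strongest case for a change is that an inference from 9.4 is weaker than a written statement. The note never mentions testing, 9.3 was left untouched, and the amendment was the natural moment to say in one sentence that the test is withdrawn. Nor does the confidence interval in 9.4.1 settle the matter. Requiring the lower limit of a 95% exact interval to exceed the null rate is a 1-sided 2.5% rule, with critical counts 27, 17 and 15 and power 69.4%, 71.8% and 70.5% at 35 subjects. It is not the test in 9.3.

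What stands is that the text is untidy. Sections 9.3, 9.4.1 and the synopsis were not aligned with the note, and one sentence would have cost nothing. What does not stand is that the choice is open after the data are seen. The listings-only rule is already written in the current protocol. Omitting the test follows that rule, and reporting one would be the departure that needs a justification. The listings also show each subject's response, so a reader of the study report can count responders whether or not a test is given.

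**Conclusion.** No change to the plan follows. This is a clerical leftover from an amendment that closed the study, and a sensible analyst resolves it by applying the 9.4 note to all efficacy output and treating 9.2.2 as a record of the original design. No stated figure is wrong: the planned 80% power comes out at 81.6%, 81.9% and 81.1%. Following 9.4 leads to listings and to no unsound conclusion, and writing down the status of the test would change no result.

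This rests on reading the 9.4 note as covering the ORR test by subject matter, which is its natural sense although it does not name the test. It also rests on the text available here. Sections 9.1 and 9.4.1 leave some details (the per-protocol population and censoring) to a Statistical Analysis Plan, and no separate plan text is at hand. Phase 2 enrollment in A1 and A2 is unknown, so the power figures at 10, 20 and 30 subjects are illustrations only.
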